### **3.3 Rationale of dose/regimen, duration of treatment**

The dose and dosing regimen of fingolimod 0.5 mg once a day has been identified in the phase III development program of fingolimod in RRMS as providing the best benefit/risk ratio and is therefore the proposed dose and regimen in the registration files to the health authorities and is the approved dose where fingolimod has been registered.

The duration of treatment of a patient in this trial is dependent on which study the patient participated in previously as well as the availability of reimbursement for commercially available fingolimod in the respective country. The end of the study is planned for 30 June 2018 (+/- 3 months). Individual patient's end of treatment visits should occur at their routine 6 monthly scheduled visit closest to 30 June 2018 to ensure all patients complete within the window for the end of the study.

Patients participating in this study will provide clinical data of 7-15 years of exposure, which will provide information on the long-term safety, tolerability and efficacy profile to help in therapeutic decision making.

[Only in the UK and Poland: The duration of treatment of a patient in this trial is dependent on what study the patient participated in previously (phase II/III vs. other). Phase II/III patients will remain in the study maximally through 30-Jun-2016. Patients, who participated in any designated global fingolimod MS trial other than phase II/III (e.g. CFTY720D2316, CFTY720D2320, etc.), were allowed to remain in the study until the drug was registered and through approximately one-year post approval or maximally through 31-Dec-12.]

[Only for Norway: The duration of treatment of a patient in this trial ran for approximately 12 months following the completion of the previous fingolimod trial or maximally through 01-Aug-2012.]

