2.5.1 Subgroups

The following subgroups are defined for subject disposition and AE analysis during fingolimod treatment period:

1. Duration of fingolimod treatment up to the end of the study part 2 (yearly interval):
 - Year 1 subgroup: patients on fingolimod treatment > 0 year (≥ 1 day)
 - Year 2 subgroup: patients on fingolimod treatment > 1 year (≥ 361 days)
 - Year 3 subgroup: patients on fingolimod treatment > 2 year (≥ 721 days)
 - Year 4 subgroup: patients on fingolimod treatment > 3 year (≥ 1081 days)
 - Year 5 subgroup: patients on fingolimod treatment > 4 year (≥ 1441 days)

- Year N subgroup: patients on fingolimod treatment > N -1 year ($\geq (N - 1) \times 360 + 1$ days)

3 Protocol Deviations

The number and percentage of patients in the enrolled set with each protocol deviation in the study part 2 will be displayed by protocol deviation category. Additionally, patients with at least one protocol deviation during the study part 2 and patients with at least one protocol deviation causing exclusion from any analysis set (deviation severity codes 0, 5, or 8) will be summarized.

The protocol deviation data will be listed as well.

Additionally, the investigator comments during the study part 2 will be listed.

4 Patient Disposition

All screen failures in the study part 2 will be listed along with their primary reason for failing screening.

The number and percentage of patients who completed the study part 2, and who discontinued the study part 2, along with the primary reason for discontinuation, will be summarized for the enrolled set. The number and percentage of patients who are expected to have month 3 follow-up visit and who returned will also be summarized. The number and percentage of patients who move to commercial fingolimod after study completion will also be included.

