To further evaluate the disposition within a particular fingolimod treatment duration, study completion and discontinuation will be summarized in separate tables based on patients' fingolimod exposure by cumulative yearly interval. Patients will be summarized within a particular yearly interval if they have been receiving study treatment for at least one day in that particular interval. For example: year 1 will consist of subjects on fingolimod treatment for at least 1 day; year 2 will consist of subjects on fingolimod treatment for at least 361 days, year 3 will consist of subjects on fingolimod treatment for at least 721 days and so on. For study completion, the number and percentage of patients who completed the study part 2, and who move to commercial fingolimod after study completion will be provided by yearly exposure group as defined above. For study discontinuation, the number and percentage of patients who discontinued the study part 2, along with the reason for discontinuation, and who move to commercial fingolimod after study discontinuation will be provided by yearly exposure group as defined above.

The patients who discontinued from the study part 2 and corresponding reasons will be listed for the enrolled set. Additionally, a similar listing will be provided for the enrolled set of patients from D2312 and D2402 studies who discontinued early from the study part 2.

5 Background and demographic characteristics

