9.1.2.2 Adverse events during the fingolimod treatment period

To further evaluate the long-term AE rate (based on patient count and percentage) within a particular fingolimod treatment duration, an analysis based on yearly intervals since first dose of fingolimod will be conducted. For summaries on this set of patients, all AEs and SAEs with onset on or after first dose date of fingolimod (among all studies) to last dose date of fingolimod are included. Each yearly interval will contain 360 days. For example: Year 1 will consist of Day 1 to Day 360, Year 2 will consist of Day 361 to Day 720, Year 3 will consist of Day 721 to Day 1080, Year 4 will consist of Day 1081 to Day 1440, Year 5 will consist of Day 1441 to Day 1800, and so on. Patients will be summarized within a particular yearly interval if they have been receiving study treatment for at least one day in that particular interval. The number and percentage of these patients who have adverse events with onset date occurring during the interval will be summarized. For example, for the Year 1 group, patients with at least one day exposure to fingolimod will be included, and AEs with onset date occurring between Day 1 and Day 360 will be summarized. For the Year 2 group, patients with at least 361 days exposure to fingolimod will be included, and AEs with onset date occurring between Day 361 and Day 720 will be summarized. The same will be done for other intervals.

Adverse events summarized by year will include the following:

- Adverse events, by yearly interval, primary system organ class, and preferred term
- Serious adverse events, by yearly interval, primary system organ class, and preferred term
- Adverse events that fulfill the risk search term, by yearly interval
- Serious adverse events that fulfill the risk search term, by yearly interval

Intervals will be included based on the length of fingolimod exposure. Risk search terms are defined in Novartis' case retrieval sheet (eCRS). Associated summaries will be presented by risk name and lower level terms.

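### The Part 2 disposition tables by exposure year repeat the overall result in the early columns and drop in the last ones by construction, so their percentages show no trend with exposure

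*SAP*

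**What the plan says.** Section 4 of the Part 2 SAP first plans an overall table of completion and discontinuation, with primary reasons, for the enrolled set. It then adds two tables by exposure. Their aim is given as: "To further evaluate the disposition within a particular fingolimod treatment duration, study completion and discontinuation will be summarized in separate tables". The grouping is by patients' "fingolimod exposure by cumulative yearly interval", with the example that "year 2 will consist of subjects on fingolimod treatment for at least 361 days".

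Section 2.5.1 gives the general cut-point for Year N as (N − 1) × 360 + 1 days. It counts all fingolimod treatment up to the end of Part 2 and sets no upper limit. The groups are therefore nested.

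In each group the discontinuation table reports "the number and percentage of patients who discontinued the study part 2, along with the reason for discontinuation". The completion table works the same way. Neither requires the stop or the completion to fall in that exposure year. Section 2.5 assigns disposition to the enrolled set, but the denominator of the by-year percentages is not stated separately.

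The yearly adverse event tables (section 9.1.2.2) use the same nested groups but limit the event: "The number and percentage of these patients who have adverse events with onset date occurring during the interval will be summarized".

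Three other places bear on how to read the tables:
- Part 2 SAP section 2 keeps D2312 and D2402 patients out of all summaries.
- Part 2 SAP section 5.3 summarises exposure before Part 2, but the disposition tables do not use it.
- Protocol section 3.3 states: "Patients participating in this study will provide clinical data of 7-15 years of exposure".

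**The concern.** The aim speaks of disposition within a given treatment duration; the rule gives disposition among everyone who reached at least that duration. A patient who stops in exposure year 9 (days 2881 to 3240) is counted as a discontinuation in each of Years 1 to 9.

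Two distortions follow. First, most summarised patients came through Part One and will have passed the early exposure years before Part 2 began. The early columns then report Part 2 stops, with reasons, under exposure years in which few or none of these patients could have left Part 2. Second, reaching a late column requires having stayed on drug until then. Whoever has just reached it during Part 2 has little Part 2 time left in which to stop, so the percentage drops for that reason alone.

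Long-term tolerability is part of the primary objective, and discontinuation by reason is one view of it. These are the only planned tables that relate discontinuation to exposure year. Taken at face value, they could suggest that discontinuation becomes rarer with longer exposure when nothing has changed.

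**Working it through.** **Plan's own figures.** The documents give no discontinuation rate or expected table, so there is no result to reproduce. The cut-points do follow from (N − 1) × 360 + 1: 1, 361, 721, 1081 and 1441 days for Years 1 to 5.

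**Inputs.** From the documents: the cut-points and nesting (Part 2 SAP sections 2.5.1 and 4) and a Part 2 length of about two years (protocol section 3.2). Assumed, because the documents do not give them: a constant discontinuation rate λ of 0.05, 0.08 or 0.12 per year, unrelated to exposure, and exposure e at Part 2 entry uniform over 5-13 years. The range of e is guided by the 7-15 years of total exposure in protocol section 3.3.

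**Formula.** Let c be the cut-point of a column in years (days / 365.25) and g = c − e the time still needed after Part 2 entry to reach it.
- g ≤ 0: the patient is in the column for certain and discontinues with probability 1 − exp(−2λ).
- 0 < g ≤ 2: the patient is in the column with probability exp(−λg). Given that, the probability of discontinuing is 1 − exp(−λ(2 − g)), so only the remaining Part 2 time counts.
- g > 2: the patient is never in the column.

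**Simplest case.** Everyone enters at 6 years and λ = 0.10. Years 1-7 show 1 − exp(−0.20) = 18.1%. Year 8 (2521 days, c = 6.90, g = 0.90) shows 1 − exp(−0.110) = 10.4%. Year 9 (2881 days, c = 7.89, g = 1.89) shows 1 − exp(−0.011) = 1.1%. The true rate is 10 per 100 patient-years throughout.

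**Entry uniform over 5-13 years, λ = 0.08.** Years 1-6 show 1 − exp(−0.16) = 14.8%. For Year 15, c = 5041 / 365.25 = 13.80, so g runs from 0.80 to 2 (width 1.1985).
- In the column: (exp(−0.0641) − exp(−0.16)) / 0.08 = 1.072, which is 1.072 / 8 = 13.4% of patients.
- Completers among them: 1.1985 × 0.8521 = 1.021.
- Discontinued: 1 − 1.021 / 1.072 = 4.7%.

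| Column | Shown as discontinued |
|---|---|
| Years 1-6 | 14.8% |
| Year 8 | 13.3% |
| Year 10 | 12.6% |
| Year 13 | 10.5% |
| Year 14 | 8.4% |
| Year 15 | 4.7% |
| Year 16 | 0.9% |

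Stops divided by Part 2 patient-years inside each interval stay at about 8 per 100.

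**Other rates, same formula.** With λ = 0.05, Year 1 is 1 − exp(−0.10) = 9.5% and Year 15 is 1 − (1.1985 × 0.9048) / ((0.9607 − 0.9048) / 0.05) = 3.0%. With λ = 0.12, Year 1 is 1 − exp(−0.24) = 21.3% and Year 15 is 1 − (1.1985 × 0.7866) / ((0.9083 − 0.7866) / 0.12) = 7.0%.

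**Clustered entry.** With λ = 0.08 and two equal cohorts entering at 5 and 9 years (each ± 0.5), the columns fall to 10.5% in Year 8. They return to 14.8% in Year 9, where only the second cohort is left and all of it is included, and fall to 2.6% in Year 12. Local rises can therefore also be artefacts.

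**Would interval-limited counts alone be enough?** No. With λ = 0.10 and entry uniform over 4-13 years, limiting stops to the interval but keeping the column N gives 0% in Years 1-4, 0.5% in Year 5 and a rise to 7.5% in Year 14. Patients who passed a year before Part 2 could not leave Part 2 in that year, yet they stay in the denominator. Dividing by Part 2 patient-years in the interval gives 9.8-10.3 per 100 in every interval that has such time, across all entry patterns tried.

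**The case against.** **The rule is disclosed.** The SAP calls the intervals cumulative and gives worked examples. Disposition among patients with at least N years of exposure is a legitimate description. This stands, and it lowers the importance. It does not make the percentages comparable across columns, and the stated aim invites that comparison.

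**Timing is not lost.** A reader might infer that the tables conceal when patients stop. The documents do not support that: the Year N count minus the Year N + 1 count is the number stopping in exposure year N, by reason, and discontinuations and dose records are also listed. Only the rate is missing, because Part 2 time at risk per exposure year is not tabulated.

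**A steady fall is not guaranteed.** A reader might infer that the percentage must decline from column to column. Early columns are flat, and clustered source studies can produce rises. A steady non-increase is certain only for counts, or if percentages are taken over the whole enrolled set. The late drop persists in every pattern tried, but in sparse columns (about 13% of patients in Year 15 above).

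**The adverse event section is not a ready template.** Those events are counted from the first fingolimod dose in any study, whereas a Part 2 discontinuation can occur only in Part 2. As shown above, copying that rule would create a different artefact.

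**Not everyone need come from Part One.** Part 2 is open to other eligible trial patients, and only D2312 and D2402 are removed from summaries. That nobody could leave Part 2 in an early exposure year is likely for most patients but not established.

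**Disposition is not a primary safety variable.** Protocol section 9.4.1 lists adverse events, laboratory values, vital signs and other investigations, all descriptive. The Part 2 SAP separately reports overall disposition by reason, adverse events leading to discontinuation and adverse event incidence rates. This stands.

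**Conclusion.** The concern holds in limited form. The by-year disposition percentages cannot be read as showing how discontinuation or completion changes with exposure. Under a constant rate of 8 per 100 patient-years they run from 14.8% in Years 1-6 to 4.7% in Year 15; at 5 and 12 per 100 they run from 9.5% to 3.0% and from 21.3% to 7.0%. These sizes rest on the assumed rates, entry exposures and two-year Part 2. The gap between the first and last columns appeared in every entry pattern tried; the shape in between depends on how entry exposure is distributed.

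This is not an error in a primary analysis, and the overall disposition table is unaffected. It is a misleading presentation in two supplementary tables, worth correcting because the correction is cheap and no other planned table gives discontinuation by exposure year.

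**What to change.** In Part 2 SAP section 4, redefine the two by-year tables. For each 360-day exposure interval, count only the Part 2 discontinuations (by reason) and completions that fall in it. Report discontinuations per 100 Part 2 patient-years accrued in that interval, with each patient entering at the exposure reached at the start of Part 2. Change the denominator together with the count. Leave the overall disposition table as it is.

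If the cumulative columns are kept as well, label them as disposition among patients with at least the stated exposure, state the denominator, and footnote that differences between columns do not show a trend with exposure.

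The cost is one SAP paragraph and the reprogramming of two tables from exposure and disposition dates already held. The downside is that early intervals will be empty or nearly so and late ones sparse.

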5.1 Core study

The core study refers to the first fingolimod MS study the patient enrolled in. The number and percentage of patients in each core study prior to transfer into the long-term follow-up study will be provided.

5.2 Demographics

Using data collected from the patient's core study, the following demographic variables will be summarized for the enrolled set: sex, age (years), age groups [<18 , 18-30, 31-40, 41-55, >55], race, ethnicity, baseline weight, baseline height, and baseline BMI. Baseline height and weight will be derived as the last non-missing assessment prior to first dose of any drug among all studies a patient has participated in. Baseline BMI will be derived based on baseline height and weight. Age will be calculated as the (core study's demographic screening or baseline visit date – patient's birth date +1) / 365.25.

Unless otherwise specified, age is presented in the listings in 3 ways: age 1 is the age at the visit where demographic data is collected (screening or baseline visit of core study); age 2 is the age at first dose of fingolimod among all studies; age 3 is the age at last dose of fingolimod.

5.3 MS disease history characteristics before enrollment in core study

Using data collected from the patient's core study, the following MS disease history characteristics will be summarized for the enrolled set: duration of MS since diagnosis in years, duration of MS since first symptoms in years, number of relapses in the last year prior to enrollment in the core study, number of relapses in the last 2 years prior to enrollment in the core study, time since the onset of the most recent relapse (in months) prior to enrollment in the core study, and duration from MS diagnosis date to last dose date of study drug (in years). The duration of exposure to fingolimod prior to first dose in the study part 2 will also be summarized for the enrolled set. Note that not all parameters are collected across all studies.

The following definitions will be used in calculations involving MS disease history characteristics: one year is defined as 365.25 days and one month is defined as 30 days.

For the MS disease history summary, the variable *Duration of MS since diagnosis* (years) will be derived for each patient as: (first dose date of any study drug among all studies a patient has participated in – the MS diagnosis date + 1)/365.25. *Duration of MS since first symptom* (years) is calculated as (first dose date of any study drug among all studies a patient has participated in – the first MS symptom date +1) / 365.25. The *time since the onset of the most recent relapse* (months) is computed as (first dose date of any study drug among all studies a patient has participated in – the most recent relapse onset date prior to enrollment in the core study + 1)/30. The duration from MS diagnosis date to last dose date of study drug (in years) is calculated as (last dose date of any study drug among all studies a patient has

participated in - the MS diagnosis date + 1)/365.25. Note that the first dose date of any study drug among all studies a patient has participated in may not be fingolimod.

5.4 MS medication history prior to enrollment in core study

For the MS medication history of disease-modifying drugs (DMDs), treatment-naïve patients are defined as those who never took MS disease-modifying medications prior to enrollment in core study. The number and percentage of treatment-naïve patients and patients who took categories of MS DMDs will be summarized for the enrolled set.

6 Study drug

6.1 Duration of exposure

The duration of exposure to fingolimod study drug during the study part 2, is defined as the number of days from first dose date of fingolimod in the study part 2 to the last dose date, excluding the days for which the patient did not take fingolimod (i.e., periods of temporary interruption). The number and percentage of patients being exposed for a minimum of ≥ 1 day, ≥ 90 days, ≥ 180 days, ≥ 360 days, etc. will be presented. Summary statistics of duration of exposure will also be provided. Patient-years of exposure will be reported and is calculated as the (sum of the total number of days on fingolimod study drug for all patients in the treatment group)/365.25. Duration of exposure to fingolimod study drug during the study part 2 will be presented for the safety set.

The fingolimod dose administration records during the study part 2 will be listed for the safety set.

7 Concomitant medication

7.1 Imputation of concomitant medication start date

Missing or partial concomitant medication start dates are imputed following the VDW MAP Module 8 ‘Concomitant Medication Start Date Imputation (#IMPUTMED)’ section (displayed below):

Concomitant Medication Start Date Imputation (#IMPUTMED)

The following table explains the notation used in the logic matrix. Please note that **missing start dates** will not be imputed.

	Day	Month	Year
Partial CMD Start Date	Not used	MON	YYYY
Treatment Start Date (TRTSTD)	Not used	TRTM	TRTY

The following matrix explains the logic behind the imputation.

	MON MISSING	MON < TRTM	MON = TRTM	MON > TRTM
YYYY MISSING	(C) Uncertain	(C) Uncertain	(C) Uncertain	(C) Uncertain
YYYY < TRTY	(D) Before Treatment Start	(A) Before Treatment Start	(A) Before Treatment Start	(A) Before Treatment Start
YYYY = TRTY	(C) Uncertain	(A) Before Treatment Start	(C) Uncertain	(B) After Treatment Start
YYYY > TRTY	(E) After Treatment Start	(B) After Treatment Start	(B) After Treatment Start	(B) After Treatment Start

The following table is the legend to the logic matrix.

Relationship	
Before Treatment Start	Partial date indicates CMD start date prior to Treatment Start Date
After Treatment Start	Partial date indicates CMD start date after Treatment Start Date
Uncertain	Partial date insufficient to determine relationship of CMD start date to Treatment Start Date
Imputation Calculation	
NC / Blank	No convention
(A)	15MONYYYY
(B)	MAX(01MONYYYY, TRTSTD+1)
(C)	IF CMDTYP1C IN (1, 3) THEN TRTSTD-1 ELSE IF CMDTYP1C IN (., 2) THEN TRTSTD+1
(D)	01JULYYYY
(E)	01JANYYYY

7.2 Imputation of concomitant medication end date

Partial or missing concomitant end dates will be imputed such that the imputed end date is the latest possible date (i.e. last day of month if day is missing, last day of year if both month and day are missing). These imputation rules will tend to consider medications with an unknown start and/or end date to be “concomitant”. See VDW MAP Module 8 variable CMDEND10 specifications for details.

7.3 Concomitant medication analyses

Concomitant medications are defined as medications, other than the study drug, that are reported during the study. All medications recorded on the CFTY720D2399 concomitant medications /significant non-drug therapies CRF will be coded using the current Hybrid DTD_DDE Dictionary. Concomitant medications and significant non-drug therapies, which are recorded in the CFTY720D2399 part 2 database and taken at any time from first dose date of fingolimod among all studies to last dose date of fingolimod + 45 days, will be summarized for the safety set by Anatomical Therapeutic Chemical (ATC) class and preferred term. The summary will show the number and percentage of patients receiving at least one drug of a particular ATC class and at least one drug in a particular preferred term (PT). To determine if any particular treatment is needed after discontinuation of fingolimod, concomitant medications and significant non-drug therapies, which are recorded in the CFTY720D2399 part 2 database and taken after last dose date of fingolimod, will be summarized in the same way as above for the follow-up set.

Note that concomitant medications which are recorded on the CFTY720D2399 part 2 concomitant medications / significant non-drug therapies CRF can include medications that may have been taken during any gap between the completion of the prior study (part 1) and enrollment into this study part 2, even if the medication is not ongoing at the time of enrollment.

All concomitant medications recorded during the study part 2 will be listed. The concomitant medications taken after study drug discontinuation but up to or after 45 days will be flagged. Records for steroid treatment of MS relapse during the study part 2 will be listed for the safety set.

8 Efficacy evaluation

The secondary objective of this study is to evaluate the long-term efficacy of fingolimod 0.5 mg in patients with relapsing forms of MS. Long-term efficacy will be assessed in MS relapse.

